7.5.1 Specific Measurements for the AD Sub-Study

Subjects in the AD sub-study will undergo the same battery of language and cognitive tasks as those in the Aphasia study, with the addition of the *Repeatable Battery for the Assessment of Neuropsychological Status* (RBANS) (147), which will be used to assess attention, language and visuospatial/constructional abilities, as well as immediate and delayed memory. Semantic fluency will be assessed by asking subjects to name as many animals and tools as possible in 1 minute intervals.

7.6 Efficacy Evaluations

No interim analyses for efficacy are planned, as previous work suggests that the maximal benefit is likely to be obtained at the 6 month endpoint and there is no additional risk to the subject after the TMS is completed.

7.7 Genetic Testing

Exploratory genetic testing will take place. Saliva samples will be collected with an OG-100 Oragene collection kit (DNA Genotek, Ontario, Canada), and DNA will be extracted using standard methodology. All subjects that consent to have genetic samples taken will have marked on their consent form that they consent to the collection and storage of their genetic sample; they will be assigned a separate coded identification number. Saliva samples will be de-identified and transported to the Penn Genomic Analysis Core for genotyping.

Storage of DNA will be conducted in the lab. DNA samples will not become part of the clinical record and will not be made available for commercial use. Identifiers for the DNA samples will not be directly traceable to any name, but rather to another coding system. The second coding system will be used to link behavioral and neurophysiologic outcomes. There are no known risks involved in saliva collection.

Once the study is complete, all samples will be destroyed.

7.8 Safety Evaluations

Subject safety will be assessed throughout the course of the study by asking subjects if they have experienced adverse effects from the interventions. Although we consider the risk to be low, TMS is the most likely study intervention to be associated with adverse effects. As any adverse effects of TMS are likely to occur at the time of stimulation, we will ask all subjects before and immediately after TMS if they note any symptoms of concern. This will be documented for each subject for each TMS session.

8 Statistical Plan

8.1 Primary Endpoint

The primary endpoint will be overall change in WAB-AQ between the first baseline visit and the 6 month follow-up visit

8.2 Secondary Endpoints

Change in naming accuracy on the PNT will serve as a secondary outcome measure

8.3 Sample Size and Power Determination

To calculate power, we started from an ambitious but realistic estimate of the population available at the participating recruitment sites. We intend to recruit up to 83 subjects to achieve a post-attrition sample size of 75. This attrition estimate is based on past experience. In previous treatment studies involving TMS (e.g., 76) and tDCS (119) we have had very low attrition; we attribute this to the fact that PWA are often very motivated by the opportunity to participate in a study with potential benefit.

Subjects (or will be allocated to TMS and CILT and sham TMS and CILT in a 2:1 ratio. Assuming a type I error rate of $\alpha=0.05$, we will have 80% power to detect a difference in mean change of 0.7 standard deviation units based on a two-sample t-test at 6 months. A 2:1 ratio was selected to provide more information about outcomes among patients randomized to TMS+CILT and as an incentive to recruitment since prospective participants are more likely to enroll in sham-controlled trials when the probability of receiving active treatment is greater. Efficiency loss associated with unequal allocation is minimal, amounting to an additional 6 participants required relative to 1:1 randomization for our design. Maher et al. (unpublished) report a standard deviation of change in the WAB AQ of 5.7 points in groups treated with Constraint Induced Language Therapy (see below). Assuming that our patients are similar, we are powered to detect a difference of 4 points in mean change in the WAB AQ between TMS+CILT and sham TMS+CILT arms. Note that our assumed effect size of 0.7 is conservative; Ren et al. (103) reported a Standard Difference of Means (a measure of effect size) of 1.26 for the general measure of severity of impairment (e.g., BDAE, Aachen Aphasia Test) based on a meta-analysis of 5 trials including a total of 96 subjects in which rTMS was compared to sham rTMS. The statistical analyses employ methods for longitudinal data in which 3 and 6 month assessments are considered simultaneously, thereby providing additional power to detect smaller effects.

8.3.1 AD Sub-Study Sample Size and Power Determination

Given the time and budget constraints that characterize a supplement, we propose to recruit to achieve an ultimate sample size of 30; given our historical attrition rate, we expect attrition of approximately 15%. The 30 subjects will be allocated to TMS + SLT and sham TMS + SLT in a 2:1 ratio, as this will provide more information about the effects of TMS and SLT and will serve as an incentive to recruitment. As noted above, loss of efficiency associated with unequal allocation is minimal relative to a 1:1 randomization for our design.

We have no preliminary data on the basis of which to calculate power. We note, however, that the meta analysis of Chen et al. (152) found a “moderate” effect size for TMS treatment for cognitive function in subjects with AD. We also note that Lee et al. (164) found a significant group effect favoring the TMS group in a study of 27 subjects with mild-moderate AD treated for impaired cognition with TMS or sham TMS and randomized in a 2:1 ratio. This project will permit us to determine an effect size that will inform sample determination for future trials.

8.4 Statistical Methods

8.4.1 Statistical Analysis of Primary Outcomes

Prior to analysis, the presence of outliers will be determined by examining descriptive statistics and graphical summaries of primary and secondary outcomes. As noted, the primary end-point will be the change in WAB AQ from the baseline for the treatment and sham groups. An intent-to-treat analysis will be performed using Linear Mixed Models for repeated-measures outcomes using outcomes at 3 and 6 months simultaneously. LMM is a regression-based approach that is suitable for repeated assessments, unlike generalized linear model regression. Additionally, unlike ANOVA, it is robust to missing data under the missing at random (MAR) assumption and sphericity assumptions. The primary outcome model will include change from baseline on the WAB AQ as the response and intervention, assessment end-point, and the interaction of intervention and end-point as fixed effects. The model will also include the baseline WAB AQ score as a predictor to increase efficiency and account for baseline imbalances in aphasia severity. A random intercept and end-point slope will be included to reflect between-subject heterogeneity in changes in WAB AQ scores. To examine possible bias in estimated intervention effects due to data missing not at random, sensitivity analyses, such as shared parameter and pattern mixture models, will be used. Secondary analyses will adjust for covariates that are imbalanced between intervention arms as well as demographic and clinical variables such as age, history of depression, lesion size, aphasia type, gender, and aphasia severity. In an exploratory analysis, we will evaluate whether there is a direct treatment effect on the WAB AQ that is not mediated by changes in response to CILT stimuli by further adjusting our primary outcome model for changes in CILT stimuli (67).

The statistical modeling of the secondary outcome (PNT) will involve similar analyses, but with items and participants modeled as random effects. Item-level response types will be analyzed separately (e.g., correct vs. incorrect; semantic error versus other response, etc.) to allow for determination of intervention effects specific to response type.

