3.1 General Design

The overall timeline for each subject's participation is indicated in Figure 1. Briefly, after randomization to treatment with TMS+CILT or sham TMS+CILT, all subjects will undergo baseline behavioral testing, neuroimaging, and genetic testing before receiving 10 treatment sessions over 2 weeks. Immediate post-treatment effects will be assessed within 4 days of the completion of therapy by repeating the baseline probes of treated and untreated stimulus sets from CILT. At 3 and 6 months after the completion of TMS, subjects will return for follow-up assessments during which the same tasks administered in Visits 1 and 2 will be repeated. Subjects who are able to undergo MRI scanning will have anatomic and fMRI scans at T5 and T22. Subjects who are not able or willing to undergo MRI will undergo CAT scan of the head.

Figure 1: Timeline for each subject

Screening Visit	Baseline 1	Baseline 2	Baseline 3	Baseline 4	Treatment 1-10	Follow-up 1	Follow-up 2 & 3	Follow-up 4, 5, 6
Visit 1	Visit 2	Visit 3	Visit 4	Visit 5	Visit 6-16	Visit 17	Visit 18-19	Visit 20-22
-Informed Consent	-WAB	-WAB	-Leftover Testing	-MRI/CAT scan	Real or Sham TMS (20 min, 1hz at 90% MT) + CILT	-CILT probe	3-months: -same as Baseline 1 & 2	6-months: -same as Baseline 1 & 2 -MRI scan
-Inclusion/Exclusion Criteria	-PNT	-Ruff Figural Pyramids and Fluency Test	-Baseline will continue into 4th and 5th visits if necessary					
-Demographics History	-Pyramids and Palm Trees	-Word and non-word repetition						
-Medical History	-Communication Confidence	-Cinderella Story						
-Medical Intake								
-Geriatric Depression Scale	Scale	-CILT baseline						
120 minutes	120-180 minutes	120-180 minutes	60-180 minutes	120 minutes	90-120 minutes	60 minutes	120-180 minutes	120-180 minutes

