6.5 Follow Up Phase of the Study

6.4.1 Visit 15

- CILT Probe: this will assess the immediate effect of TMS + CILT on the treated words from CILT.

The anticipated time of this visit is 60 minutes.

The follow-up visit may be conducted via tele-assessment.

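### The exploratory direct-effect model in 8.4.1 adjusts for an undefined post-randomization CILT change and for no shared cause except baseline WAB AQ, so its treatment coefficient need not be a direct effect

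*Combined protocol and SAP*

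**What the plan says.** Section 8.4.1 states the aim: "In an exploratory analysis, we will evaluate whether there is a direct treatment effect on the WAB AQ that is not mediated by changes in" the response to CILT material. The method is "further adjusting our primary outcome model for changes in CILT stimuli", with a mediation textbook cited in support.

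The model being extended has "intervention, assessment end-point, and the interaction of intervention and end-point as fixed effects", plus a random intercept and slope. Its one baseline covariate is the WAB AQ: "The model will also include the baseline WAB AQ score as a predictor to increase efficiency". A wider set, "demographic and clinical variables such as age, history of depression, lesion size, aphasia type, gender, and aphasia severity", belongs to separate secondary analyses and is not said to enter the direct-effect model. The sensitivity analyses named there concern missing data only: "To examine possible bias in estimated intervention effects due to data missing not at random, sensitivity analyses, such as shared parameter and pattern mixture models".

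On the mediator, section 3.1 says: "Immediate post-treatment effects will be assessed within 4 days of the completion of therapy by repeating the baseline probes of treated and untreated stimulus sets". The Visit 15 entry under section 6.5 is narrower: "this will assess the immediate effect of TMS + CILT on the treated words from CILT". CILT stimuli are also tested at Visits 1 and 2 (6.3.1, 6.3.3), and that battery is repeated at 3 and 6 months (6.4.2, 6.4.4). Section 8.4.1 does not say which time point or which item set defines the change.

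**The concern.** Randomization makes the arms comparable. It does not make subjects with large and small CILT gains comparable within an arm. Both measures are language tests in the same people, so lesion extent or learning ability could move both. Conditioning on CILT change then mixes the treatment effect with differences in that factor. The path from TMS to CILT gain is part of the trial's own rationale: section 1.2.2.2 couples TMS with therapy so that each strengthens the other.

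The open definition adds two problems. If the change is taken at the same visit as the WAB, the time order of mediator and outcome is unclear. And the two item sets ask different questions: adjusting for treated-item change asks whether benefit goes beyond the trained cards, while adjusting for untreated-item change removes some of the generalization itself.

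At stake is the reading of one exploratory result about mechanism, not the efficacy conclusion.

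**Working it through.** **The plan's own figure.** Section 8.3 gives 80% power for 0.7 SD with 75 subjects at 2:1 and alpha 0.05 (two-sided assumed). With 25 sham and 50 TMS, SE = √(1/25 + 1/50) = 0.245 SD, and 0.7/0.245 = 2.86. Power is 81.5% by the normal approximation and 80.5% by the t-test. Then 0.7 × 5.7 = 3.99, the stated 4 points. The figure reproduces. The documents give no figure for the direct-effect analysis.

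**Model for the check.** T is treatment, M is CILT change, Y is WAB AQ change and U is a factor not in the model. M and Y have within-arm SD 1.

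- M = aT + cU + error
- Y = τT + bM + dU + error, with true direct effect τ = 0

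Regressing Y on T and M without U gives M the coefficient b + cd. The T coefficient is therefore τ + ab − a(b + cd) = τ − acd, so the **bias is −acd**. It is zero if a, c or d is zero.

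**Inputs.** The SD of 5.7 and the 25/50 split follow from section 8.3. The values of a, b, c and d are all assumptions. The 0.7 used for a is borrowed from the WAB AQ power calculation and is not an estimate for CILT.

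**Base result.** With a = 0.7 and c = d = 0.5: −0.7 × 0.5 × 0.5 = −0.175 SD, and × 5.7 = −1.0 point, a quarter of the 4-point target. Simulation at 25 vs 50 gave −0.178 SD. A two-visit random-intercept mixed model with treatment-by-visit, baseline and M gave −0.172 SD. Both return about 0 when U is adjusted for. Over a from 0 to 1.0 and c = d from 0.3 to 0.7, the bias runs from 0 to −0.49 SD (−2.8 points).

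**Baseline WAB AQ correlated with U.** If the correlation is r, the bias becomes −acd(1 − r²)/(1 − c²r²). In the base case:

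- r = 0.5: −0.7 × 0.25 × 0.75/0.9375 = −0.14 SD
- r = 0.7: −0.7 × 0.25 × 0.51/0.8775 = −0.10 SD

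**Measurement error in CILT change.** With reliability ρ, the bias is ab(1 − ρ) − aρcd. With a = 0.7 and b = 0.3:

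| c = d | ρ = 1 | ρ = 0.8 | ρ = 0.7 |
|---|---|---|---|
| 0.3 | −0.06 | −0.01 | +0.02 |
| 0.5 | −0.18 | −0.10 | −0.06 |
| 0.6 | −0.25 | −0.16 | −0.11 |

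The sign can reverse.

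**Against sampling noise.** In the base case (b = 0.3) the residual variance is 1 − 0.55² = 0.6975. The sum of squares for T is 25 × 50/75 = 16.67. The share of T explained by M is 0.49 × 0.222/(1 + 0.49 × 0.222) = 0.098, which leaves 15.03. SE = √(0.6975/15.03) = 0.215 SD, or 1.2 points. The base-case bias is a little under one SE. In simulation with τ = 0 the rejection rate was 12.7%, against 4.7% with U adjusted for. With τ = 0.49 SD, power was 29% against 71%.

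**The case against.** The strongest reply is that this is one sentence describing an analysis labelled exploratory, that every bias figure rests on assumed paths, and that the plan already guards against simple item training. Section 5.2.5 rules out overlap between CILT and WAB stimuli and keeps an untreated card set to measure generalization. The proposed covariates do not measure learning ability or effort, and three of them already appear in the secondary analyses. All of this stands, and it limits the point.

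A reader might go further and infer that the analysis is biased towards no direct effect, so that the trial would wrongly put its benefit down to item training. The documents do not support that. The downward direction needs TMS to raise CILT gain, the shared factor to act the same way on both gains, and CILT change to be measured with little error; no reliability is given. Section 8.4.1 attaches no such conclusion to the coefficient. Nor can the −1.0 point be taken as an estimate for this trial.

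What the reply does not remove is the method itself. The model omits plausible shared causes that the trial already collects, leaves the mediator undefined, and plans no check on mediator-outcome confounding. A textbook citation does not supply those choices.

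**Conclusion.** The point holds as a minor improvement to an exploratory analysis. The treatment coefficient, after adjustment for CILT change, is a direct effect only if nothing outside the model drives both CILT and WAB gain and CILT change is well measured. The plan neither states nor examines these conditions. Under assumed paths of 0.7, 0.5 and 0.5 the bias is about −0.18 SD (−1.0 point), falling to between −0.14 and −0.10 SD if baseline WAB AQ correlates 0.5 to 0.7 with the factor, and to −0.06 SD at a mediator reliability of 0.7. With weaker confounding and that reliability it turns slightly positive. Neither size nor direction can be settled from the documents. The primary intent-to-treat estimate and the sample size are not affected.

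**What to change.** In section 8.4.1:

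1. Define the mediator as the change from baseline to the immediate post-treatment probe, which falls within 4 days of therapy and so precedes the 3- and 6-month WAB.
2. Name the item set: treated items, with untreated items analysed separately. First reconcile section 3.1 with the Visit 15 entry on which sets are probed.
3. Add baseline CILT accuracy, lesion size, age and aphasia type to this model.
4. State the assumption of no unmeasured mediator-outcome confounding.
5. Report a sensitivity analysis over a range of residual mediator-outcome correlation and of mediator reliability.

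The cost is a few degrees of freedom at 75 subjects and a little analysis work. The protocol already schedules the baseline measurements; the untreated-item analysis depends on the probe covering that set. Because the covariates only reduce the confounding, the result should be reported as exploratory and dependent on its assumptions.

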8.4.2 Identifying Predictors of Treatment Response

As in our primary analyses, we will use Linear Mixed Modeling (LMM) to identify the strongest clinical/linguistic predictors of response to TMS+CILT as compared to sham TMS+CILT from among variables like chronicity, severity, gender, depression severity, naming accuracy, apraxia of speech, core semantics, and sentence processing. Although we will be underpowered for formal tests of interaction given our moderate sample size, we will refit our primary endpoint model by adding interactions of the intervention indicator and potential predictors of response to therapy to see which are suggestive of differential intervention effects. We expect that these analyses will illuminate the clinical/linguistic predictors of treatment response, thereby defining the ideal “target population” for a future Phase 3 clinical trial.

Network Neuroscience measures of response to TMS+SLT

Subjects who can undergo MRI will have studies obtained prior to treatment and at 6 months after the completion of TMS. We will construct brain networks for each individual based on their baseline and post treatment BOLD fMRI data. We will use both the AAL (132) and Glasser et al. (40) parcellations and subject-specific lesion masks to exclude lesioned areas prior to atlas registration within each subject. Then, we will extract time series data from each region following modern preprocessing practices designed to reduce the influence of motion on BOLD time series (24). Across all pairs of region time series, we will compute wavelet coherence, which is well-suited for non-stationary data such as BOLD fMRI (128), to construct an adjacency matrix A that represents the pairwise coherence across all regions within the frequency band 0.01 to 0.10 Hz,

which is robust to physiological noise and evinces reliable functional network organization (44). We will constrain our analysis to the functional connections observed among regions identified to be involved in language processing (34) and their homotopic regions. Within each subject, we will compute a within-subjects t-test for elements (connections) in A₃ (final timepoint) versus A₁ (baseline) in the language and homotopic systems corrected for multiple corrections using a false discovery rate correction with a nominal corrected p-value of 0.05. This will allow us to detect the connections most modified by treatment and determine whether mechanism 1, 2, or 3 is supported.

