Aphasia is an acquired disorder of language that occurs in approximately 30% of individuals with stroke and impacts approximately 1 million Americans (see NINDS.NIH.gov). Persons with aphasia (PWA) suffer greater disability and utilize more health care resources than individuals with stroke without aphasia (33); Boehme et al (16), for example, estimated that aphasia adds \$2.16 billion annually to the cost of acute stroke care. The economic burden of aphasia can persist for years, not only due to direct costs of care, but also because of lost wages and productivity. Furthermore, the social isolation felt by PWA leads to enormous personal and psychological costs. Current treatments for aphasia are only modestly beneficial (17, 59). Many individuals with moderate or severe aphasia after stroke continue to suffer significant impairment despite therapy. The fundamental objective of this proposal is to demonstrate that Transcranial Magnetic Stimulation (TMS) paired with language stimulation will improve chronic aphasia. More specifically, we seek to demonstrate that TMS combined with speech-language therapy (SLT) will improve language performance more than SLT alone. Additionally, we will employ modern techniques for network analyses of neuroimaging data collected before and after TMS and SLT to determine the mechanism(s) by which this is achieved. Finally, we seek to identify the predictors of response to TMS, making use of genetic testing. To achieve these goals, we propose the first double-blind, placebo-controlled investigation of TMS combined with SLT that is sufficiently powered to assess the efficacy of the therapy. If the treatment proves successful, our work will set the stage for a Phase 3 trial of the efficacy of TMS with SLT in the treatment of chronic aphasia.

AD Sub-study Introduction

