2.2 Secondary Objectives (if applicable)

- To determine the mechanism(s) by which TMS improves language function using modern techniques for network analyses of neuroimaging data collected before and after TMS and CILT.
- To identify the predictors of response to TMS, including using genetic analysis.

3 Investigational Plan

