6.4.4 Visit 18, 19 & 20 (6-month follow-up)

The same battery of tasks administered in visits 1 and 2 will be administered in these visits which will occur at 3 months after the end of TMS. The anticipated time of these visits is 120-180 minutes. Additionally, for those subjects who had an MRI at the beginning of the study, a repeat MRI scan will be performed using the same acquisition parameters described below. The ADRS will also be collected again at the 6-month follow-up timepoint. The ADRS is completed by the participant's caregiver.

The 6-month follow-up visits may be conducted via tele-assessment.

For in-person follow-up visits (i.e. not conducted via tele-assessment), the final day of the follow-up testing may include a brief tele-assessment, time permitting and with the subjects approval. This tele-assessment will consist of some combination of the tests (listed under Visits 1 and 2) conducted via video software; study personnel will conduct this tele-assessment from a nearby room.

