8.4.3 AD Sub-Study Network Neuroscience

Subjects who can undergo MRI will have scans obtained prior to treatment and at 6 months after the completion of TMS. All other details are as stated above, however, subject-specific lesion masks will not be relevant.

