12.2 Benefits

The objective of the study is to determine if TMS paired with CILT improves chronic aphasia; subjects randomized to the TMS+CILT treatment group may benefit from the treatment. We note that the study is also potentially of benefit to those who randomize to the sham TMS+CILT group as they will receive two weeks of CILT, an accepted form of speech therapy for which there is evidence of efficacy. The study is also of potential benefit to other subjects with chronic aphasia as it may identify an effective therapy for this disabling condition.

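### The imaging plan tests only final against baseline connectivity; with no TMS-versus-sham contrast, a change cannot be attributed to TMS

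*Combined protocol and SAP*

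**What the plan says.** The network part of Section 8.4.2 builds a coherence matrix for each subject from the baseline scan and another from the post-treatment scan, restricted to language regions and their homotopes. The test is then: "Within each subject, we will compute a within-subjects t-test for elements (connections) in" the final matrix versus the baseline matrix, FDR-corrected to 0.05. The conclusion follows directly: "This will allow us to detect the connections most modified by treatment and determine whether mechanism 1, 2, or 3 is supported". Section 8.4.3 carries the same analysis into the AD sub-study, apart from lesion masks.

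The question this is meant to answer is set in two places. The Introduction says "we seek to demonstrate that TMS combined with speech-language therapy (SLT) will improve language performance more than SLT alone", and that imaging will be used for "network analyses of neuroimaging data collected before and after TMS and SLT to determine the mechanism(s) by which this is achieved". Section 2.2 states the secondary objective as "To determine the mechanism(s) by which TMS improves language function".

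Two design facts bear on it. Section 12.2 describes the "sham TMS+CILT group as they will receive two weeks of CILT, an accepted form of speech therapy for which there is evidence of efficacy". Section 6.4.4 says that "for those subjects who had an MRI at the beginning of the study, a repeat MRI scan will be performed", with no restriction by arm.

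**The concern.** The objective is about what TMS adds, and the trial has a randomised sham arm that isolates it. The stated imaging test does not use that arm. Two weeks of CILT, six months of elapsed time and a second scanning session could each change connectivity in both arms. A connection that changes for any of these reasons would meet the plan's criterion for having been modified by treatment, and would count towards one of the candidate mechanisms.

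At stake is the mechanistic conclusion, a named secondary objective of a trial intended to prepare for Phase 3. Imaging is not among the endpoints in Sections 3.3 or 8.1–8.2, so the WAB-AQ result does not depend on it.

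**Working it through.** **1. Is there an arm contrast for imaging anywhere?**

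| Place | Response | Arm term? |
|---|---|---|
| 8.4.1, primary model | Change in WAB-AQ | Yes |
| 8.4.1, secondary outcome | PNT | Yes (similar model) |
| 8.4.2, predictors of response | Primary endpoint model refitted with clinical and linguistic predictors | Yes |
| 8.4.2, network analysis | Connectivity, final vs baseline | No |
| 8.4.3, AD network analysis | As 8.4.2 | No |
| 3.1, 3.1.3, 6.4.4, 7.3 | Scan timing and acquisition only | – |

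No passage compares connectivity change between arms.

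**2. What each comparison estimates.** For one connection, let c be the mean change common to both arms (CILT, time, retest) and t the added effect of TMS. Allocation is 2:1 (Section 3.1.4).

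- TMS arm, final minus baseline: c + t
- Sham arm, final minus baseline: c
- Both arms pooled: (2/3)(c + t) + (1/3)c = c + 0.67t
- TMS change minus sham change: (c + t) − c = t

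Within a single subject, c and t cannot be separated. If t = 0, the pre-post comparisons still return c.

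**3. Illustration of the consequence.** The documents give no c, so it is assumed here: c = 0.2, 0.3 or 0.5 SD of change, with t = 0. Two-sided alpha is 0.05 per connection before FDR, using the noncentral t with noncentrality c√n for the one-sample tests.

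| Assumed c (SD) | Pooled pre-post rejects, n = 75 | Pooled, n = 45 | TMS arm alone (50) | Sham alone (25) | Significant in TMS, not in sham | Between-arm test |
|---|---|---|---|---|---|---|
| 0.2 | 0.40 | 0.26 | 0.28 | 0.16 | 0.24 | 0.05 |
| 0.3 | 0.73 | 0.50 | 0.55 | 0.30 | 0.38 | 0.05 |
| 0.5 | 0.99 | 0.91 | 0.93 | 0.67 | 0.31 | 0.05 |

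The sixth column is the TMS-arm probability times one minus the sham probability; at c = 0.3, 0.548 × (1 − 0.302) = 0.38. Running the pre-post test by arm and comparing significance is therefore no remedy. The larger TMS arm tilts that comparison towards TMS when TMS does nothing.

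**4. What a between-arm test could detect.** Section 8.3 gives the trial's only power figure: 80% for 0.7 SD at 75 subjects, 2:1. It reproduces: noncentrality = 0.7/√(1/50 + 1/25) = 0.7/0.245 = 2.86 on 73 df gives 80.5%. That figure concerns WAB-AQ. The number with two usable scans and the plausible effect on connectivity are not stated, so the table borrows 0.7 SD and varies the number scanned.

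Baseline adjustment multiplies the SD of change by √((1 + r)/2), where r is the baseline–final correlation (equal variances assumed); at r = 0.5 this is 0.866. Degrees of freedom are n − 2 unadjusted and n − 3 adjusted. The 17/9 row is 30 × 0.85 = 25.5, split about 2:1.

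| TMS/sham | Unadjusted, α 0.05 | Adjusted, r = 0.5 (range r = 0.3 to 0.7) | Unadjusted, α 0.001 | Adjusted, r = 0.5, α 0.001 | 95% CI half-width, unadjusted / adjusted (SD of change) |
|---|---|---|---|---|---|
| 50/25 | 81% | 90% (94–86%) | 30% | 46% | 0.49 / 0.42 |
| 30/15 | 58% | 70% (77–65%) | 11% | 19% | 0.64 / 0.55 |
| 20/10 | 42% | 52% (58–47%) | 5% | 8% | 0.79 / 0.69 |
| 17/9 | 37% | 47% (52–42%) | 4% | 6% | 0.85 / 0.74 |

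The 0.001 column stands in for a stricter threshold after FDR. Effect size matters most: at 50/25, unadjusted at 0.05, power falls from 81% at 0.7 SD to 52% at 0.5 SD and 23% at 0.3 SD.

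**The case against.** **The test may be a first-level step.** The wording is per subject, and a group-level arm comparison may simply have gone unwritten. That is a fair reading, and the plan nowhere says the arms will be pooled, so c + 0.67t describes only one way of carrying it out. But no second step is given, and the mechanism conclusion is drawn from this test directly. Under any of these readings the sham arm is unused.

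**Treatment may mean the TMS+CILT package.** Possibly. A pre-post comparison still cannot separate the package from time and retest, and Section 2.2 asks about TMS.

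**The remedy is not only an added arm term.** This stands in part. Each subject has one baseline and one final matrix, hence one pair of values per connection and no replication for a t-test within a subject. The unit of replication must be stated, and a per-connection arm test may differ from what was intended. Lesion masking will also leave fewer subjects for some left-hemisphere connections, and two parcellations are used, so the FDR family needs defining. The lesion precedes treatment, so masking reduces numbers without biasing a randomised comparison.

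**The illustrative numbers rest on assumptions.** Correct, and they are labelled so. The structural point in step 2 needs none of them.

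**It is only a secondary, unpowered aim.** True, and it limits the severity. It does not make the stated inference valid.

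**Conclusion.** The concern holds. The plan's only inferential imaging test cannot answer its own mechanism question, because it lacks the randomised comparison that separates TMS from what both arms receive. This follows from the stated test and from CILT being given in both arms, with no numerical assumption. How much change would be misattributed cannot be determined, as the documents give no CILT, time or retest effect on connectivity; the rejection rates above are conditional on assumed shared changes. Mechanisms 1 to 3 are not defined in the text available, possibly because a figure is missing, and this is not counted against the plan. The point should be corrected before the imaging data are analysed. It does not touch the primary efficacy inference.

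**What to change.** Add a between-arm test to Section 8.4.2:

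- For each language or homotopic connection, compare change in coherence (final minus baseline) between TMS+CILT and sham+CILT, preferably adjusting for baseline coherence.
- Apply the FDR correction to the arm p-values, and say whether it runs within or across the two parcellations.
- Base any statement about a TMS effect on connectivity on this contrast. Label it secondary or exploratory, and keep within-arm change as descriptive.
- Report the number per arm, by connection where masking reduces it, with confidence intervals for the arm difference.
- If the existing pre-post test is kept, state its unit of replication.

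Extend this to Section 8.4.3 only after the AD scan time is reconciled. Section 8.4.3 says "Subjects who can undergo MRI will have scans obtained prior to treatment and at 6 months after the completion of TMS", Section 3.2.3 puts the scan at or after the 12-week visit, Section 6.4.5 lists it under the 12-week visits, and Section 3.2 labels it T17. Sections 4.9 and 8.3.1 also differ on whether 30 is the AD number before or after attrition; the 17/9 and 20/10 rows cover both readings if every remaining subject is scanned twice.

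The cost is analysis wording; the scans are already planned without restriction by arm. The price is lower power than a pre-post test. With the numbers likely to be scanned, a null arm contrast would be inconclusive and should be reported as such.
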